Overall Study Design: Interventions will address three primary areas to improve vaccination uptake: (1) process (text messages); (2) teachable moment messaging (motivational interviewing); and (3) barrier elicitation and reduction (electronic survey with tailored questions/prompts). In our selection of potential interventions, we will use the Community Preventive Services Task Force (CPSTF)⁹ and the NIH Behavior and Social Sciences Research-Coordinating Committee Rapid Working Group on COVID-19 Vaccine Communication guide, among other resources.¹⁰ We will work with the NIH RADxSM-UP Coordination and Data Collection Center (CDCC) to ensure collection of Common Data Elements.

Table 2. Experimental conditions in the 2³ factorial design for the COVID-19 vaccine intervention

Condition	Factor		
	Process Improvement	Teachable Moment Messaging	Barrier Elicitation and Reduction
1	No	No	No
2	No	No	Yes
3	No	Yes	No
4	No	Yes	Yes
5	Yes	Yes	Yes
6	Yes	Yes	No
7	Yes	No	No
8	Yes	No	Yes

Outcome metrics characterizing SARS-CoV-2 vaccine uptake. Our **primary outcome** will be intention to receive a COVID-19 vaccine post-intervention. We will measure this with the question “How likely are you to get an approved COVID-19 vaccine?” and “If you have received 1 dose of the Janssen vaccine or 2 doses of the Moderna or Pfizer vaccine, how likely are you to get an approved booster shot?” We will compare intention to receive a COVID-19 vaccine or booster among those receiving the interventions compared to those not receiving the intervention (see details on analysis below).

Our **secondary outcome** will be vaccine uptake, including self-report of receiving an initial dose of any approved vaccine, two doses of Pfizer or Moderna vaccines, or a booster of any approved vaccine. We will request the manufacturer of the vaccine and the approximate dates the vaccine was received from the participant.

Aim 2.1. Pilot Implementation.

Study Design. Participants at the pilot sites will be randomized to receive a text message and/or education message (detailed below) delivered through a tablet or no intervention. We will also conduct a pilot of motivational interviewing messages that are tailored based on antibody test results (or lack of testing if the participant declines an antibody test).

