We will collect a survey using Research Electronic Data Capture (REDCap) software (Nashville, TN) to allow for descriptive statistics, assessment of study outcomes, and ensure the randomization is balanced regarding these characteristics.

Intervention Procedure

1. Screening Form to identify eligibility for the study. This will include age, ability to read and speak English, vaccine status and dose information (see eligibility criteria), and having symptoms of COVID-19 or positive test for COVID-19 infection in the previous 14 days. The screening form will include the following symptoms as having active COVID-19: fever, chills, cough, shortness of breath, difficulty breathing, lack of energy/general tired feeling, muscle or body aches, headache, new loss of taste or smell, sore throat/congestion/runny nose, nausea, vomiting, or diarrhea, abdominal pain, or skin rash.

2. Obtain consent and HIPAA authorization and allow an opportunity for questions.
3. Brief demographic questionnaire (race, ethnicity, sex, county of residence) and questions to assess intention to receive a COVID-19 vaccine.
4. Conduct interventions. All participants will have the opportunity to receive antibody testing using a finger stick (using the same methods as in the CATCH-UP Study, IRB #12582). After the antibody test is done and participants are waiting for the results (about 15 minutes), the participants will receive the interventions. If participants decline the antibody test, the interventions will begin once consent, HIPAA, and the brief demographic questionnaire are complete.
 - a. **Text message.** Participants will be randomized to either receive 1) a text message encouraging COVID-19 vaccination (treatment) or no text message (control). This factor will last less than 1 minute.
 - b. **Tailored messaging.** Participants will be randomized to receive 1) educational messaging about COVID-19 vaccines (treatment) or 2) an attention control educational message not related to COVID-19 (control). This will be delivered on a tablet through RedCap. This factor will last around 10 minutes.

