6. We will send participants a RedCap survey link through text message or email 30 days and 60 days after the intervention to assess intent to be vaccinated for COVID-19 and vaccine uptake, allowing time for both doses of the Pfizer and Moderna, single dose of Jansen’s COVID-19 vaccine, or boosters of vaccines to be delivered. We will also send up to three daily reminders to the participant to complete the common data elements survey if they did not complete it after the intervention.
7. For participants who agree, we will contact up to 60 participants to participate in an evaluation interview to help the personnel determine what did and did not work well during the intervention. This will be a 30 minute to one hour interview.

Aim 2.2. Full implementation.

Study Design. Participants will be randomized to a 2 x 2 x 2 fully crossed factorial design, creating 8 conditions to evaluate the contribution of each intervention component in an initial pilot/feasibility study. For each intervention site, we will collect a brief demographic survey through Research Electronic Data Capture (REDCap) software (Nashville, TN) to allow for descriptive statistics and ensure the randomization is balanced regarding these characteristics.

Intervention Procedure

All interactions with participants will occur through a tablet or through verbal communication.

1. Screening Form to identify eligibility for the study. This will include age, ability to read and speak English, vaccine status and dose information (see eligibility criteria), and having symptoms of COVID-19 or positive test for COVID-19 infection in the previous 14 days. The screening form will include the following symptoms as having active COVID-19: fever, chills, cough, shortness of breath, difficulty breathing, lack of energy/general tired feeling, muscle or body aches, headache, new loss of taste or smell, sore throat/congestion/runny nose, nausea, vomiting, or diarrhea, abdominal pain, or skin rash.
2. Obtain consent and HIPAA authorization and allow an opportunity for questions.
3. Brief demographic questionnaire (race, ethnicity, sex, county of residence) and questions to assess intention to receive a COVID-19 vaccine.

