 6. We will send participants a RedCap survey link through text message or email 30 days and 60 days after the intervention to assess intent to be vaccinated for COVID-19 and vaccine uptake, allowing time for both doses of the Pfizer and Moderna, single dose of Jansen's COVID-19 vaccine, or boosters of vaccines to be delivered. We will also send up to three daily reminders to the participant to complete the common data elements survey if they did not complete it after the intervention.
 7. For participants who agree, we will contact up to 60 participants to participate in an evaluation interview to help the personnel determine what did and did not work well during the intervention. This will be a 30 minute to one hour interview.

At all events, key personnel will also conduct a field observation of how the events flow, including external factors such as weather or logistical problems and where challenges to implementing the study or recruiting participants occurred. We will also conduct evaluation focus groups with event site staff to determine what did and did not work during the event.

We expect to recruit 2000 participants over the entire study period (Aim 2.1 and 2.2).

Factorial design. In a factorial research design, two or more independent variables are concurrently examined within the same trial. The three factors are crossed with one another to create a total of eight experimental conditions. An equal number of participants are randomly assigned to each condition, using a random number generator. This is not an 8-arm randomized controlled trial, but instead allows for an efficient examination of main effects for each variable in a sample of 2000 participants (including Aim 2.1 and Aim 2.2).

This approach allows examination of three key treatment development questions in a much more time-efficient and economical manner by simultaneously performing three studies within the single trial. This achieves power to detect between-group differences that is equivalent to performing three separate randomized trials. Investigators who are providing the intervention and conducting analysis will be not be masked to study assignment due to challenges in maintaining the masking in an educational intervention. For all sites, including Aims 2.1 and 2.2, we expect to recruit 2000 participants.

Identifiers might be removed and the de-identified information may be used for future research without additional informed consent from the subject.

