Evaluation. Global questions will be explored in the program evaluation, including: 1) What are potential barriers and facilitators to “real-world” implementation of the interventions?; 2) What problems are associated with delivering the interventions, and how might they translate to improving implementation processes?; 3) What potential modifications to the interventions could be made to maximize implementation?; and 4) Among the interventions that were implemented, which appeared most promising? *Implementation process metrics* will be assessed by conducting a process evaluation for deployment of interventions to increase vaccine uptake. To organize process findings, we will generate a comprehensive list of patient and community implementation outcomes aggregated through the common taxonomy of the Proctor et al. evaluation framework.^{11, 12} The evaluation also will incorporate measures from CFIR,¹³ which has been shown to be effective for guiding successful implementation.^{14, 15}

Research team members will visit the community sites or meet through videoconference to conduct five additional focus groups with multiple respondents, including the community members involved in the intervention, to assess acceptability, cultural relevance, and possible barriers. We will also interview participants who agreed to an interview in the consent form for evaluation of the intervention. Findings will help clarify processes of care and perceptions of barriers and facilitators. The focus group guide will prompt participants to discuss their practice context as it relates to their experiences with implementing each of the intervention components, and participants will be probed regarding challenges and facilitators they face when implementing each component. To evaluate whether the selected intervention(s) improved vaccine uptake in the pilot study, our team will evaluate aggregate vaccination data for the catchment area of the community site through the Oklahoma State Department of Health. The final product will summarize barriers and facilitators for implementation and provide a thorough picture of the implementation process, including feasibility, acceptability, and fidelity of intervention implementation that can inform future large-scale research.

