As a secondary analysis, we will compare vaccine coverage among counties with an intervention compared to counties without intervention to see whether coverage increased in the study counties using a chi-square test. We will use publicly available data from the Oklahoma State Department of Health and/or Centers for Disease Control and Prevention for this analysis.

Sample size and power calculations. Power calculations are based on our primary analysis, which is to assess the effect of each intervention component on increased intention to receive a COVID-19 vaccine immediately after the intervention. This is a two-sample comparison between participants that receive one intervention component and those that receive the control. Our pilot implementation will include a single site with an estimated 500 participants.

Our outcome of interest is also assessed at 30 and 60 days follow-up to measure intention to receive a COVID-19 vaccine, which allows us to use a longitudinal generalized estimating equations approach wherein power is proportional to the within-site

correlation. Using PASS v16, we assume the intra-cluster correlation within each site is 0.01. Our power analysis is based on data from both pilot and full implementation of the study results. Assuming a minimum n=167 participants per site for a minimum of sites, a Type 1 error rate of 0.05, and an estimated standard deviation of 5, we have over 80% power to detect a mean difference of 20.

Data and Safety Monitoring Plan

Drs. [name] and [name] assure that oral informed consent is obtained prior to conducting the focus groups (Aim 1) and written informed consent and HIPAA authorization are obtained for the intervention (Aim 2) prior to performing any research procedures, that all subjects meet eligibility criteria, and that the study is conducted according to the IRB-approved research plan.

Study data are accessible at all times for the PI/PD to review. [name] will review the study conduct weekly and the PI/PD will review the study conduct on a monthly basis. Study conduct will include accrual, drop-outs, and protocol deviations. The PI/PD will review adverse events individually in real-time and in aggregate on a weekly basis.

COLLECTION AND REPORTING OF SAEs AND AEs

For this study, the following standard AE definitions are used:

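### The Evaluation text assigns the question of whether the interventions raised vaccine uptake in the pilot to catchment-area totals, which pool the randomised arms and cannot answer it

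*Combined protocol and SAP*

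**What the plan says.** All references are to the combined protocol and SAP.

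- **Section D, Evaluation:** "To evaluate whether the selected intervention(s) improved vaccine uptake in the pilot study, our team will evaluate aggregate vaccination data for the catchment area". The data come from the state health department. The paragraph names no comparison area, baseline or time window.
- **Section D, Aim 2.1, Study Design:** "Participants at the pilot sites will be randomized to receive a text message and/or education message", or no intervention. Step 4 of the procedure randomises each person to text or no text, and to the vaccine message or an attention control. Motivational interviewing is piloted in step 4c and is not described there as randomised.
- **Section D, Factorial design (written for the eight conditions):** "An equal number of participants are randomly assigned to each condition, using a random number generator".
- **Section I, Sample size:** "Our pilot implementation will include a single site with an estimated 500 participants".
- **Section D, Outcome metrics, and Aim 2.1, step 6:** self-reported uptake is the secondary outcome, and participants are surveyed "30 days and 60 days after the intervention to assess intent to be vaccinated for COVID-19 and vaccine uptake".
- **Section I, Aim 2 Analysis:** analyses are by intention to treat. Outcomes at 30 and 60 days are compared cross-sectionally, by chi-square if binary, and a GEE model is added.
- **Section I, secondary analysis:** a separate comparison sets counties with an intervention against counties without one.

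**The concern.** The Evaluation sentence asks a causal question and names a data source that carries no arm label. The text-message group, the educational-message group and the controls were recruited at the same site and are counted in the same area figure, together with every resident who never attended. No contrast within that figure corresponds to a randomised comparison.

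Without a comparator or period, the remaining reading is a change over time in one area. That would absorb any campaign, change in eligibility or seasonal pattern in local vaccination. The risk runs both ways: a flat area trend could be reported as no effect, and a rising one as success of the interventions. The same Evaluation section asks which intervention looked most promising, and a pooled total cannot rank components.

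**Working it through.** The plan gives no figure for a catchment-area effect, a catchment population or an expected uptake effect, so there is no figure of its own to reproduce. Its one power statement concerns intention.

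**1. Can the total separate the arms?** With randomisation of individuals inside a site, coverage in area A is (vaccinated text recipients + vaccinated non-recipients + vaccinated non-participants) / population. Only the sum is observed. This step needs no assumed number.

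**2. How far is an effect diluted?** Change in coverage = (people affected × uptake effect) / catchment population. Inputs: 500 pilot participants (Section I); equal allocation, assumed to hold in the pilot too, so 500/2 = 250 per level of a factor; an assumed effect of 10 points.

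- One factor works: 250 × 0.10 = 25 extra vaccinations.
- Up to all 500 are affected, for example through the non-randomised motivational interviewing: 500 × 0.10 = 50 extra.

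| Assumed catchment | 25 extra | 50 extra | Binomial SE at 30% coverage |
|---|---|---|---|
| 10,000 | 0.25 points | 0.50 points | 0.46 points |
| 50,000 | 0.05 | 0.10 | 0.20 |
| 250,000 | 0.01 | 0.02 | 0.09 |

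The SE is sqrt(0.30 × 0.70 / population). The 30% is the statewide fully vaccinated figure in Section B and is used only as an illustration. The SE excludes any secular trend.

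Other assumptions widen the range, from 0.003 points (25 extra in 800,000) to 1.0 point (100 extra in 10,000, which is 500 × 0.20).

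**3. Would a comparison area rescue it?** Suppose an equal-sized area at 30% coverage were added (two-sided 0.05, counting rejections in the favourable direction only, so the floor is 2.5%). Power with 25 extra vaccinations is 6% at 10,000 and 4% at 50,000. With 50 extra it is 12% and 5%.

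**4. What can the randomised comparison do?** SE = sqrt(p1(1−p1)/n1 + p2(1−p2)/n2); power = Φ(difference/SE − 1.96). Base rates are assumed, and response is complete unless stated.

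- One factor gives 10 points, 250 v 250, 15% v 25%: SE 3.5 points, power 80%. If half respond (125 v 125), 51%.
- The same at 30% v 40%: SE 4.2 points, power 65%. At 30%, 80% power needs a difference of about 12 points.
- Either component alone gives the full 10 points and the two do not add. In a 2×2, half of the 250 without the text still received the educational message, so the factor contrast is 25% v (15% + 25%)/2 = 20%: SE 3.7 points, power 27%. Any component against none (375 v 125, 25% v 15%) has SE 3.9 points and power 73%.

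The randomised contrast is thus not always well powered, but it estimates the right quantity.

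**The case against.** The strongest reply is that the plan already holds the right analysis. Uptake is a declared secondary outcome, it is collected from pilot participants at 30 and 60 days, and the Aim 2 Analysis is not limited to Aim 2.2. That stands. A reader might infer that pilot uptake will be judged only from area data and that a real effect would go unseen; the documents do not support this.

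Second, the sentence sits in a programme evaluation, among focus groups and process measures, and Section A (Aim 2.2) does express a goal at catchment level. Area data suit that goal and do not depend on self-report or survey response. This is a good reason to keep them as context. It does not make them evidence of effect, which is what the sentence claims.

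Third, the meaning of the pilot is uncertain. Aim 2.2 is also described as conducted "in an initial pilot/feasibility study", and Aim 2.1 speaks of pilot sites where Section I has one. If the whole study is meant, the arithmetic on 500 does not apply. The structural fault remains, because Aim 2.2 also randomises individuals. Taking the plan's minimum of 167 per site with half treated, 167/2 × 0.10 = 8.35 extra vaccinations, or 0.08 points in 10,000 and 0.017 in 50,000. If the sentence merely points to the county comparison, a comparator exists, but the arms are still pooled within each county.

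Fourth, a reader might infer that area totals will steer the choice of components. The plan speaks of feedback from Aims 1 and 2.1 and of observation notes used to revise the messages. It does not say that area data feed that choice.

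**Conclusion.** The point holds as a fault in one sentence. That sentence assigns a causal question to data that pool the randomised arms, with no comparator or period, although data able to answer it are already being collected. This follows from randomisation within site and rests on no assumed number.

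The size of the dilution is conditional: 0.25 to 0.5 points in 10,000 and 0.05 to 0.1 points in 50,000, for an assumed 25 to 50 extra vaccinations. It would be tempting to say that the effect shrinks to hundredths of a point. With 25 extra that needs a catchment of roughly 25,000 to 250,000, and the documents give no size.

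It would also overstate the case to set the area analysis against a randomised comparison with 80% power for the same effect. That figure applies only if a single factor gives 10 points, from a 15% base with complete response; it is about 65% from a 30% base. Nor can the randomised data answer everything: motivational interviewing is not described as randomised in Aim 2.1, so its effect there cannot be estimated by arm.

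**What to change.** Replace the Evaluation sentence with wording such as: *The effect on vaccine uptake will be assessed by the comparison of participant-level uptake at 30 and 60 days between randomised groups, as set out under Aim 2 Analysis, for each randomised factor (text message and educational message in Aim 2.1; all three factors in Aim 2.2), with differences and 95% confidence intervals. Vaccination data for the catchment area will be described as local background, and no effect will be inferred from them.*

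In the same edit, say which stage is meant by the pilot study, reconcile the single pilot site with the plural used in Aim 2.1, and define the catchment and the period to be described.

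The cost is a sentence or two of text. The follow-up surveys and between-group tests are already planned; only the differences and intervals are added.

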4. Conduct interventions. Participants will be randomized to receive or not receive each of the interventions described below. Participants may be randomized to receive all three factors (treatment), all three control factors, or any combination of treatment/control as defined below (see Table 2). All participants will have the opportunity to receive antibody testing using a finger stick (using the same methods as in the CATCH-UP Study, IRB #12582). After the antibody test is done and participants are waiting for the results (about 15 minutes), the participants will receive the interventions.
 - a. **Text message.** Participants will be randomized to either receive 1) a text message encouraging COVID-19 vaccination (treatment) or no text message (control). This factor will last less than 1 minute.

- a. **Tailored messaging.** Participants will be randomized to receive 1) educational messaging about COVID-19 vaccines (treatment) or 2) attention control educational message not related to COVID-19 (control). This will be delivered on a tablet through RedCap. This factor will last around 10 minutes.
 - b. **Motivational interviewing.** Participants will be randomized to receive feedback on their antibody tests in these two methods: 1) receive a motivational interview following the 5A's strategy (Ask, Advise, Assess, Assist, Arrange) following a semi-structured format (treatment) or 2) interpretation of antibody test results and encouragement of vaccine uptake (as per usual standard practice) (control). Personnel will make notes regarding any deviations from the semi-structure script or assigned treatment arm (e.g., some participants may decline to discuss the vaccine). This factor will last around 5 minutes.
5. Once the interventions are complete, the participants will complete a brief exit survey that includes questions about their intention to receive a COVID-19 vaccine or booster and to request their contact information for future contact and mailing/distribution of gift card (if mailing or emailing is needed). Participants will also be asked to complete a survey required by NIH to report common data elements, with a link sent through text message or email, with follow-up daily for up to three days after the initial survey invitation is sent, and at 30 and 60 days post intervention if the participant has not responded (in tandem with the follow-up survey in #6 below). This will complete the intervention.

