COVID-19 incidence, particularly among underserved minority and rural Oklahomans. Oklahoman's are also reporting SARS-CoV-2 vaccine hesitancy and signs of slowing vaccine uptake, with increased hesitancy among American Indian and rural populations. The project aims to work with ongoing community testing events to implement interventions to improve vaccine uptake among Oklahoma's underserved populations.

I. Statistical Methods

Aim 1 Analysis. Digitally recorded focus groups will be securely uploaded to protected servers and transcribed using NVivo Transcription. Transcriptions will be team coded for conceptual themes using QSR NUDIST Vivo12 Pro for Windows.¹⁶ Investigators will develop a code book. Throughout the coding process, qualitative data will be categorized, connections made between categories, and core categories identified and systematically linked to other categories. Focus group data will inform intervention selection and needed modifications for community acceptability/relevance.

Aim 2 Analysis. All analyses are intent-to-treat. Outcome measures will be assessed at baseline, 30 days, and 60 days follow-up. At the outset, we will examine the frequency distributions of all variables. We will compare the baseline characteristics to assess whether randomization distributed covariates evenly. We will determine whether there is differential dropout and consider developing probability-of-completion weights to obtain unbiased estimates of treatment effect.

The primary analysis will assess the effects of each intervention component in terms of its association with the primary outcome (intent to receive a COVID-19 vaccine immediately after the interventions are completed). Cross-sectional analyses will be conducted for outcomes assessed at 30 and 60 days. For binary outcomes, chi-square tests will be used to compare the outcomes between groups. For continuous outcomes, two-sample t-tests or Wilcoxon rank sum tests, whichever is more appropriate, will be used to compare between groups. A longitudinal analysis using Generalized Estimating Equations (GEE) techniques will also assess the overall impact of the intervention by including data from all follow-up time points.

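### The plan commits to no non-response correction for the 30- and 60-day outcomes, and a comparison of drop-out rates could miss responders who differ by arm

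*Combined protocol and SAP*

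**What the plan says.** All references are to the combined protocol and SAP.

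- **Analysis set.** Section I, Aim 2 Analysis, states "All analyses are intent-to-treat". It gives no rule for missing outcomes under that principle.
- **Missing data.** The same section has one provision: "We will determine whether there is differential dropout and consider developing probability-of-completion weights". It does not say what counts as differential, what follows if nothing is found, or which variables enter the weights. No imputation or sensitivity analysis is mentioned.
- **Tests.** "Cross-sectional analyses will be conducted for outcomes assessed at 30 and 60 days", with chi-square tests for binary outcomes and t-tests or Wilcoxon tests for continuous ones. A GEE combines the follow-up times. Weights are not mentioned for any of these.
- **Timing.** The section lists "Outcome measures will be assessed at baseline, 30 days, and 60 days follow-up". The exit survey is not in that list, although the primary outcome is measured on it.
- **Data collection.** Section D, Aims 2.1 and 2.2, asks about intention before the interventions (step 3) and again straight after them, when "the participants will complete a brief exit survey that includes questions about their intention to receive a COVID-19 vaccine or booster" (step 5). The 30- and 60-day surveys are links sent by text or email (step 6). Uptake is self-reported and is the secondary outcome.

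**The concern.** Follow-up depends on participants answering a link. The daily reminders in step 6 are for the common data elements survey; none is stated for the 30- and 60-day survey. Section G allows the gift card to be handed over at the event and states no separate incentive for follow-up.

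A comparison of drop-out rates shows how many people answer in each arm. It does not show who answers. If a vaccine message makes persuaded people more likely to answer and puts off hesitant people, the two shifts can offset. The rates then match while responders in one arm are keener on vaccination than in the other. A chi-square test on responders would read that as an effect on uptake.

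Baseline variables alone cannot fully repair this, because the components are meant to change intention after randomisation. Exit-survey intention is measured after that change and before remote follow-up begins. It is a plausible predictor of both response and uptake.

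Section D (Factorial design) also says that those doing the analysis will know the assignments. Leaving the weights to be considered later therefore gives unmasked analysts a choice after they have seen the drop-out pattern.

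**Working it through.** **The plan's own figures.** The documents give no expected response rate, uptake rate or drop-out bias, so there is nothing to reproduce. The power statement in Section I concerns the primary analysis and is not used here.

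**Inputs from the documents.** 2000 participants over Aims 2.1 and 2.2, allocated equally, give about 1000 per level of a factor. The pilot is put at 500 and its procedure does not list motivational interviewing as randomised, so that factor has about (2000 − 500)/2 = 750 per level.

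**Assumptions.** No true effect. In both arms 45% intend to be vaccinated at exit. Uptake is 30% in intenders and 3% in others, so true uptake is 0.45 × 0.30 + 0.55 × 0.03 = 15.15%. Clustering by site is ignored.

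**Formulas.** With r1 and r0 the response probabilities of intenders and others:

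- overall response R = 0.45·r1 + 0.55·r0
- share of intenders among responders s = 0.45·r1 / R
- uptake among responders = 0.03 + 0.27·s
- rejection probability = Φ(z − 1.96) + Φ(−z − 1.96), where z = difference / √(2·p̄(1 − p̄)/m), p̄ is the mean of the two responder uptakes and m is responders per level

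| Arm | r1 / r0 | R | s | Responder uptake | Difference from control |
|---|---|---|---|---|---|
| Control | 0.60 / 0.300 | 0.435 | 0.621 | 19.8% | – |
| Treatment, case A | 0.65 / 0.259 | 0.435 | 0.672 | 21.2% | 1.4 points |
| Treatment, case B | 0.70 / 0.218 | 0.435 | 0.724 | 22.6% | 2.8 points |

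**Type I error.**

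- 1000 per level (m = 435): case A has standard error 0.0274, z = 0.51, rejection 8.0%. Case B has 0.0277, z = 1.01, rejection 17.2%.
- 750 per level (m = 326): 7.3% and 14.1%.

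**Does a rate check detect it?** In 6000 simulated trials per case at 1000 per level, a two-sample test of response rates flagged about 5% to 6% of trials, which is chance level.

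**Does weighting on exit intention help?** Responders within each arm-by-intention group have the right uptake by assumption, so reweighting returns 0.45 × 0.30 + 0.55 × 0.03 = 15.15% in each arm. In simulation the weighted mean difference was within 0.03 points of zero and type I error was about 5%. The standard error of the difference fell from about 0.027 to 0.021, and the same fall appeared when both arms had the 0.60/0.30 pattern.

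**Same response pattern in both arms.** With 0.60/0.30 in both arms and no effect, the bias in the difference is exactly zero. If the component raises intention from 45% to 50%, responder uptake is 21.0% against 19.8% (1.24 points unrounded), the true difference is 0.27 × 0.05 = 1.35, and the bias is −0.1 points.

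**Sensitivity to the assumptions.** Take instead 50% response overall, 50% intenders, uptake 40% and 5%, and control response of 50% in both groups. Treated response from 55%/45% to 70%/30% gives spurious differences of 1.75 to 7.0 points and rejection of about 10% to 71% at 1000 per level.

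**The case against.** The strongest reply is that the text is under-specified rather than wrong. A reader might infer that weights are used only if drop-out rates differ and that unweighted responder tests follow otherwise. The sentence does not say so: it promises to determine and to consider, with no stated condition. Differential drop-out could also mean who drops out, in which case the check would look for this very problem. That stands. What remains under either reading is that nothing is committed and no variable is named.

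A reader might also infer that exit-survey intention goes unused. It does not: it is the primary outcome, and the GEE for intention may include it as a time point. The accurate statement is that it is not named for non-response correction. Nor can it be assumed complete, since Section H (Protection Against Risk) lets participants skip questions or join only parts of the study.

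The mechanism can be doubted too. The bias needs response to depend on arm and intention jointly, and both cases above offset exactly by construction. In Aim 2.2 the control for motivational interviewing itself includes encouragement to vaccinate, and the text message takes under a minute. Nothing in the documents supports any particular arm-specific shift. That stands as a limit on the size, not on the logic.

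Finally, weighting succeeds above because simulated response depends only on arm and exit intention. If people answer because they have since been vaccinated, these weights will not remove the bias.

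**Conclusion.** The concern holds for the secondary 30- and 60-day outcomes and the GEE. The plan commits to no correction. If its check is a comparison of rates, that check can pass while responders differ by arm, and the most useful available predictor is not named.

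The size is unknown. About 1.4 to 2.8 points, with type I error of about 8% to 17% (7% to 14% with 750 per level), rests on assumed response and uptake rates, equal overall response and no true effect. Other assumed rates give more. An identical response pattern in both arms gives none under the null.

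Two stronger conclusions are not supported. One is that the trial's main result is at risk: the primary outcome is taken on site on the same day, so non-response to later links essentially does not touch it. The other is that the intention-to-treat label necessarily fails, or that uptake levels will be overstated. Both depend on who responds, which the documents do not tell us. Responder uptake of 19.8% against a true 15.15% in the control example follows from assuming that intenders answer more often.

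The change is still worthwhile: it uses data already collected, and in the examples it also improved precision when the difference was unbiased.

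**What to change.** Amend Section I, Aim 2 Analysis, before follow-up data are analysed:

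1. State that the 30- and 60-day comparisons and the GEE use inverse-probability-of-response weights, or equivalent multiple imputation, whatever the drop-out check shows.
2. Specify one response model containing all randomised factors, baseline intention, exit-survey intention, factor-by-exit-intention interactions, prior vaccine status, demographics and site. Models fitted separately for each factor would give several weight sets and no single set for a GEE with three factors.
3. Report response by arm and exit intention.
4. Keep the unweighted responder analysis as a sensitivity analysis.
5. Add a not-at-random sensitivity analysis, because the weights do not correct response that depends on later uptake.

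No new data are needed. The cost is revised wording, a little extra analysis and some dependence on the response model.
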